8.5. Other Analyses

The following data will be summarized and listed by treatment and in accordance with the current Pfizer data standards: demographics, subject disposition, primary diagnosis, medical history, previous and concomitant medications.

Baseline characteristics will be summarized and tabulated, including the following data:

- PAH treatment at entry: n(%) for PAH-treatment naïve and on PAH-treatment;
- Etiology of PAH: n(%) for idiopathic, and secondary to CTD/surgical repair;
- WHO pulmonary hypertension functional class: n(%) for each class;
- Descriptive summary statistics (n, mean, SD, median and range) for:
 - 6MWD;
 - BORG score.

Number (%) of subjects with at least 80% compliance will be tabulated by study treatment and subject dosing records will be listed.

Baseline PAH background therapy and changes in the PAH background therapy will be listed and summarized.

If appropriate, exploratory analyses of primary and secondary endpoints by subgroup of gender, race, or ethnicity will be performed.

9. INTERIM ANALYSIS AND DMC RECOMMENDATION

Protocol Sections 9.5 and 9.6 pre-specified two interim analyses after 50% and 75% of the required number of events (143 deaths) have occurred and detailed on DMC responsibilities/recommendations, respectively.

A planned interim analysis was conducted after 50% of the required number of events (72 deaths) occurred. The Data Monitoring Committee (DMC) reviewed the results of the interim analysis based on the primary efficacy endpoint of time to death. DMC provided recommendation that the study be stopped as the primary objective (non-inferiority of the 80 mg TID arm vs 5 mg TID arm) had been met. The DMC also expressed a concern regarding the mortality in the 5 mg TID arm. Pfizer accepted the DMC recommendation; all participating sites were notified of DMC recommendation and the end of study activities were initiated.

As a result of the DMC recommendation, all subjects currently on sildenafil 5 mg TID were to be placed on prescription sildenafil or an alternative PAH treatment at the Investigator's discretion. However, there are sites with subjects who do not have post-study PAH treatment options available, for those subjects, investigators were advised to switch, in a blinded manner, the dose for subjects receiving 5 mg (TID) to 20 mg (TID) until the end the study. (See Protocol Appendix 6 for further details end of study activities and on continuity of study treatment and dose adjustment (5 mg to 20 mg (TID))).

An unblinded team, with no connection to the conduct of study, was created to communicate with DMC and regulatory agency. Study team continued to be blinded until final database lock.

9.1. Sensitivity Safety Analysis

If a subject is switched from 5 mg to 20 mg, they will be reported under their randomized treatment group for all efficacy analyses but will be reported under the treatment they first receive for all safety analyses. In addition, a sensitivity safety analysis for deaths, major AE and SAEs will be conducted on the subgroup of subjects that switched from 5 mg to 20 mg only.

In summary, study analyses tables will present data by treatment as follows:

- All efficacy analysis will be presented with 3 randomized arms (5 mg, 20 mg, 80 mg).
- All safety analysis will be presented with 3 actual treated arms (5 mg, 20 mg, 80 mg).
- Sensitivity analysis for the subgroup of patients who switch from 5 mg to 20 mg, for major safety endpoint (ie, deaths, AEs, SAEs) will be presented with 4 treated arms (5 mg, 20 mg, 80 mg, 5-20 mg).

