9.1. Sample Size Determination

Total of 429 subjects will be randomly assigned into sildenafil 5 mg TID, 20 mg TID and 80 mg TID treatment group with 143 subjects in each treatment group.

This non-inferiority study is powered at 90% to test the following hypotheses at overall significance level of 0.025 (1-sided):

- H_0 : hazard ratio (80 mg TID /5 mg TID) ≥ 2 ;
- H_1 : hazard ratio (80 mg TID /5 mg TID) < 2 .

The sample size of the study is calculated based on the following assumptions:

- Equal mortality rate of 15% at 2-years for each arm;
- Accrual rate of 100 subjects/year;
- Two interim analyses with O'Brien-Fleming approach possibly rejecting H_0 or H_1 ;
- Estimated 20% drop-out rate (including lost to follow-up).

With the estimated recruitment rate, the study is expected to complete enrollment in about 4.3 years with total duration of about 7.7 years to reach required number of events (deaths) of 143.

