9.2. Efficacy Analysis

9.2.1. Analysis of Primary Endpoint

The primary efficacy analysis will be conducted using the intent-to-treat (ITT) population. All events occurring up until the end of the trial, including events observed from discontinued patients, will be included in the primary efficacy analysis. The efficacy analyses will also be conducted using the per-protocol (PP) population as sensitivity analyses.

Treatment comparison will be conducted using Cox proportional hazard regression model stratified by PAH treatment at entry of the study (PAH-treatment naïve vs. on PAH treatment) and etiology of PAH (idiopathic vs. secondary to CTD/surgical repair). If the 1 sided upper confidence limit of the hazard ratio (80 mg TID/5 mg TID) is less than 2, then the null hypothesis that the mortality rate in the 80 mg TID is worse than double the rate in

5 mg TID will be rejected. In case that the hazard ratio is statistically significantly less than 1, then superiority of 80 mg TID over 5 mg TID will be claimed. Treatment comparison will also be evaluated using the exact test as sensitivity analysis.

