5. ANALYSIS SETS

5.1. Full Analysis Set

The intent-to-treat population (ITT) will consist of all randomized patients treated with study treatment. The primary efficacy analysis will be conducted using ITT population.

5.2. 'Per Protocol' Analysis Set

The Per-protocol population (PP) will consist of randomized subjects who receive at least 1 dose of study treatment and contribute at least 1 post-baseline visit. The time to event endpoint for this PP will consist of all events that occur while the subjects are on study treatment without major protocol deviations/violations through 35 days after the last dose of the study treatment, since randomization. This collection period (from randomization to

35 days after the last dose of the study treatment) will also be applied to other efficacy endpoints with PP analyses.

The efficacy analyses of primary and secondary endpoints will be conducted using the per-protocol (PP) population as sensitivity analyses.

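### Follow-up after the 5-to-20 mg switch counts as 5 mg in every efficacy analysis, the per-protocol set included, so no efficacy analysis isolates time on the randomised dose

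*SAP*

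**What the plan says.** Protocol Appendix 6 gives the sequence. The planned interim analysis used 72 deaths with data cut on 30 May 2020. The DMC recommended stopping because non-inferiority was met, and it raised a concern about mortality on 5 mg. A second letter, of 30 July 2020, told sites whose subjects had no post-study option to hold a visit before 15 August 2020. At that visit 5 mg was replaced by a blinded 20 mg kit, while 20 mg and 80 mg stayed as they were. Treatment then runs to an End of Treatment Visit with no fixed date.

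For switched subjects, SAP 9.1 states that "they will be reported under their randomized treatment group for all efficacy analyses". Protocol 9.2.1 adds: "All events occurring up until the end of the trial, including events observed from discontinued patients, will be included in the primary efficacy analysis". SAP 5.2 defines the PP time-to-event endpoint as "all events that occur while the subjects are on study treatment without major protocol deviations/violations through 35 days after the last dose", with no stop at a change of dose. SAP 5.6 leaves the PP exclusions to be listed before database lock and does not name the switch. The only analysis that separates switchers is the safety table in SAP 9.1, with a fourth column for 5-20 mg.

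**The concern.** Once the 5 mg arm is closed, continuing on-treatment follow-up is on 20 mg or 80 mg only, yet part of it is analysed as 5 mg. A PP analysis would normally show the result on the assigned dose. Here it does not, because its window follows study treatment of any dose. The on-treatment death definition in SAP 8.1 (up to 7 days after the last study dose) does not separate doses either.

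At stake are the final estimates: the 80 vs 5 mg hazard ratio and its interval, the superiority claim that SAP 4.2 allows, time to first clinical worsening, and the secondary 20 vs 5 mg comparison in SAP 4.1 and 8.1. These are also the estimates by which readers will judge the DMC's concern about 5 mg.

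**Working it through.** **The plan's own figure.** Protocol 9.1 tests "H_0 : hazard ratio (80 mg TID /5 mg TID) ≥ 2" at one-sided 0.025 with 90% power and requires 143 deaths. The Schoenfeld formula gives 4 × (1.960 + 1.282)² / (ln 2)² = 88 deaths in the two compared arms for a fixed design; Freedman's gives 95. Two thirds of 143 is 95.3. Simulating the stated boundaries at 95.3 deaths gives 90.2% power with futility stopping. So 143 is the three-arm total and it reproduces. Nothing below changes it.

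**Which side of 1 the interim estimate lay on.** Of 72 deaths, 72 × 2/3 = 48 are expected in the two arms, so SE(log HR) = 2/√48 = 0.289. Crossing p < 0.0015 (z = 2.968) needs log HR < 0.693 − 2.968 × 0.289 = −0.164, that is HR < 0.85. If all 72 deaths fell in those two arms, the limit would be 0.99. The estimate therefore favoured 80 mg.

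**Expected post-switch deaths.** "Equal mortality rate of 15% at 2-years for each arm" implies a hazard of −ln(0.85)/2 = 0.0813 per year. The documents give neither the number switched nor their follow-up; I assume 10-40 subjects and 0.25-1 year.
- Low: 10 × 0.25 × 0.0813 = 0.2 deaths.
- High: 40 × 1 × 0.0813 = 3.3 deaths.

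**Effect on the hazard ratio.** Let P be pre-switch person-years per arm, T post-switch person-years in the 5 mg arm, and h5, h20, h80 the hazards. The rate analysed as 5 mg is (h5·P + h20·T)/(P + T). The apparent ratio is h80 divided by that. I set h5 + h80 = 2 × 0.0813, so 48 deaths give P = 48/0.1625 = 295 years per arm.

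Example: true HR 0.50, h20 = h80, T = 40. Then h5 = 0.1083 and h80 = 0.0542. The rate analysed as 5 mg is (32.0 + 2.17)/335.4 = 0.1019, and the apparent HR is 0.0542/0.1019 = 0.532.

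| 20 mg hazard | T (years) | True 0.50 | True 0.70 | True 0.85 |
|---|---|---|---|---|
| equal to 80 mg | 2.5 | 0.502 | 0.702 | 0.851 |
| equal to 80 mg | 10 | 0.508 | 0.707 | 0.854 |
| equal to 80 mg | 40 | 0.532 | 0.726 | 0.865 |
| 0.7 × 80 mg | 40 | 0.542 | 0.745 | 0.893 |
| 1.2 × 5 mg | 40 | 0.488 | 0.684 | 0.830 |

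A Cox-type weighting agrees to within 0.001. If 20 mg equals 80 mg, the largest shift (0.50 to 0.532) is ln(0.532/0.50) = 0.062 on the log scale, or 0.062/0.289 = about a fifth of a standard error.

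**20 vs 5 mg.** The apparent ratio is h20(P + T)/(h5·P + h20·T). For T > 0 this always lies between h20/h5 and 1. Dilution of this comparison therefore needs no assumption about the 20 mg hazard.

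**The case against.** The strongest reply is that nothing decisive depends on this. Analysis by randomised arm is the correct ITT rule. The formal decision was taken on a pre-switch data cut, so a time-to-death comparison free of the switch has already been run. The likely shift is small against the standard error. All of that stands. What is missing is a commitment to report such an analysis beside the final results and to extend it to clinical worsening and the other dose pairs.

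The reply can also point to the four-column safety table. A subject must be alive to switch, so every death in the 5-20 mg column is a post-switch death, and the count will be visible. But the table gives no hazard ratio. It also sorts whole subjects by a later event, which takes survivors' pre-switch time out of 5 mg and makes 5 mg look worse. Nor does the open exclusion list in SAP 5.6 settle the PP question: a switch directed by the protocol is not naturally a deviation, and the SAP does not name it.

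A reader might go further and infer that making the arms alike biases the trial toward non-inferiority. The documents do not support this. No post-switch event could enter the decision, and with an estimate below 1 a pull toward 1 makes 80 mg look less favourable. A reader might also take the direction for 80 vs 5 mg as certain, or expect a larger effect on clinical worsening. The first depends on a 20 mg hazard that is not given. The second cannot be sized, because no worsening rate is given and a switcher with an earlier worsening event adds nothing further.

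**Conclusion.** The gap is real but modest. Post-switch time and events are counted as 5 mg in both the ITT and PP efficacy analyses. The ITT rule should stay, the non-inferiority decision is untouched, and no design figure changes.

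If the 20 mg hazard lies between those of 5 mg and 80 mg, or equals that of 80 mg, the 80 vs 5 mg hazard ratio is pulled toward 1. In the case of equality the shift is about 0.001 to 0.03. If 20 mg carried 0.7 times the 80 mg hazard, the shift could reach about +0.045. If it carried 1.2 times the 5 mg hazard, the ratio would move away from 1 by about 0.02. The 20 vs 5 mg comparison is diluted in every case.

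These sizes rest on the assumed 10-40 switchers, 0.25-1 year of follow-up, 48 pre-switch deaths in the two arms, equal person-time and constant hazards. The sponsor holds the true counts and can replace the assumptions.

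**What to change.** 1. Add sensitivity Cox analyses of death and of time to first clinical worsening for all three dose pairs. Censor every arm at one common calendar date before any switch: 30 July 2020, or the 30 May 2020 interim cutoff.
2. State in SAP 5.2 that, for subjects moved from 5 mg to 20 mg, PP follow-up ends on the date of the first switched dose, with no 35-day extension beyond it. Leave the meaning of last dose unchanged for everyone else, so that the planned two-week 20 mg start in the 80 mg arm is unaffected.
3. Report the number switched and their post-switch person-time.

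The cost is a few lines of SAP text and reruns of existing Cox code. A few late events drop out of the sensitivity analyses; the ITT main analysis keeps them. SAP 9 says the study team stayed blinded until final database lock, so these rules could be set before lock without knowledge of results by arm.

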11. APPENDICES

Appendix 1. CLASSIFICATION OF PAH TREATMENT AT ENTRY (programmatically)

PAH Treatment Naïve:

Subjects were randomized as PAH Treatment Naïve and data are missing for PREVIOUS DRUG TREATMENT FOR PRIMARY DIAGNOSIS

or

Subjects met one of the criteria below based on data recorded on PREVIOUS DRUG TREATMENT FOR PRIMARY DIAGNOSIS:

- If there are no records for subjects when Con med Class = ""PREVIOUS DRUG TREATMENT FOR PRIMARY DIAGNOSIS"

Or

- Con med Class = ""PREVIOUS DRUG TREATMENT FOR PRIMARY DIAGNOSIS" and the concomitant medication preferred term(CMDECOD) is like ("AMBRISANTAN", "BERAPROST", "EPOPROSTENOL", "ILOPROST", "MACITENTAN", "OPSUMIT", "REVATIO", "SILDENAFIL", "TADALAFIL", "TRACLEER", "VELETRI", "VENTAVIS", "ZEPAHX")

and

- Calculation of duration since start of treatment (tr01sdt-cmstrt)+1 value is <28 days then patient is PAH treatment naïve.

On PAH Treatment:

Subjects met the criterion below based on data recorded on PREVIOUS DRUG TREATMENT FOR PRIMARY DIAGNOSIS:

- if CMCLAS = "PREVIOUS DRUG TREATMENT FOR PRIMARY DIAGNOSIS"

and

- The concomitant medication preferred term is like ("AMBRISANTAN", "BERAPROST", "EPOPROSTENOL", "ILOPROST", "MACITENTAN", "OPSUMIT", "REVATIO", "SILDENAFIL", "TADALAFIL", "TRACLEER", "VELETRI", "VENTAVIS", "ZEPAHX")

and

- Calculation of the duration since start of treatment (tr01sdt-cmstrt)+1 value is ≥ 28 days then patient is on PAH treatment.

Subjects will be put in the stratum that reflects clinical reality. Patients will be analyzed under the correct determined stratum, ie, stratum determined by clinical data that they should have been randomized.

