			
 • Added two new references to Section 10. • Added algorithm for calculation of PAH at treatment stratification in Appendix 11.1. • All SAS & StatExact Codes are presented in Appendix Sections 11.2.1-11.2.6. • Updated Appendix 11.2.1 and 11.2.4 on SAS code for the Cox Proportional Model and MMRM analysis models, respectively. • Added visit window for secondary and tertiary endpoints to Appendix 11.3. 
As of protocol amendment 2, dated 28 August 2020 the following changes has been incorporated:
 
 • Added to Section 8.2 a sensitivity analyses for time to first adjudicated clinical worsening events. • Added a new Section 9 for DMC review of unblinded interim analysis and its recommendation. This recommendation led to an update regarding study conduct and currently includes a new safety sensitivity analysis for death and SAEs. • Added sensitivity safety analysis for subjects who were switch from 5 mg to 20 mg treatment (Section 9.1).
--	--	--	--

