5.5. Randomization Stratification Misallocations

- Randomized as PAH Treatment Naïve but should have been randomized as On PAH Treatment.
- Randomized as On PAH Treatment but should have been randomized as PAH Treatment Naïve.

Classification of a patient into these stratum will be done programmatically and is presented on [Appendix 1](#).

Subjects will be put in the stratum that reflects clinical reality and will be analyzed under the correct determined stratum, ie, stratum determined by clinical data that they should have been randomized. A data listing will be provided for subjects with randomization stratification error.

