6.3. Covariates

The analyses of the primary and secondary endpoints will be performed using the following two randomization stratification factors as covariates:

- PAH treatment at entry (PAH-treatment naïve vs. on PAH-treatment);
- Etiology of PAH (idiopathic vs. secondary to CTD/surgical repair).

The analyses of 6MWD will also include baseline results as a covariate.

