7. HANDLING OF MISSING VALUES

Missing data will not be imputed. For 6MWD at Month 6 and 12, mixed model for repeated measure method (MMRM) will be used for statistical analyses for treatment comparisons. For MMRM, all available data in Month 6 and 12 will be included in the analyses and any missing data are assumed missing at random. Details of the analyses are described in [Section 8](#).

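### The program rule in SAP Appendix 1 that replaces the randomised PAH-treatment stratum can, as written, misplace or fail to place some eligible subjects

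*SAP*

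**What the plan says.** Protocol section 3 stratifies randomisation by PAH treatment at entry (naïve or on treatment) and by etiology. SAP 5.5 then replaces the randomised treatment stratum with a derived one: "Subjects will be put in the stratum that reflects clinical reality and will be analyzed under the correct determined stratum". The derivation is in SAP Appendix 1. The SAP change log places it among the changes that followed a blind data review: "Added algorithm for calculation of PAH at treatment stratification in Appendix 11.1".

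To be classed as on treatment, a subject needs three things:
- a record in the class for previous drug treatment of the primary diagnosis;
- a listed name, where the test begins "The concomitant medication preferred term is like ('AMBRISANTAN" and runs to 13 terms;
- the timing condition "Calculation of the duration since start of treatment (tr01sdt-cmstrt)+1 value is ≥ 28 days then patient is on PAH treatment".

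A subject is classed as naïve in any of three ways:
- "Subjects were randomized as PAH Treatment Naïve and data are missing for PREVIOUS DRUG TREATMENT FOR PRIMARY DIAGNOSIS";
- no record in the class at all ("If there are no records for subjects when Con med Class");
- a listed drug for which the same date difference is below 28 days.

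Neither branch uses a stop date or an ongoing flag. SAP 7 adds: "Missing data will not be imputed".

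**The concern.** The derived stratum overrides the randomised one, so the Appendix 1 text is the working definition of a stratification factor. It should place every eligible subject in one stratum, in line with a factor defined at entry. As written it may not. The drug list does not match the protocol's own drug names, and the only date tested is the start of the drug.

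The factor is widely used. Protocol 9.2.1 stratifies the primary Cox model by it. SAP 6.3 states: "The analyses of the primary and secondary endpoints will be performed using the following two randomization stratification factors as covariates". It also enters the exact logrank test, the MMRM for 6MWD, the Van Elteren test for BORG score, the by-stratum tables and the listing of stratification errors. At stake are mislabelled strata and subgroups and, if unplaced subjects are left with a missing stratum, their loss from stratified analyses.

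**Working it through.** The plan gives no figure on this point, so the check is to apply the rule as written.

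**Inputs.** From SAP Appendix 1: the 13 terms and V = tr01sdt − cmstrt + 1, with a cut at 28. I read tr01sdt as the first study dose and cmstrt as the drug start. From the protocol:
- ambrisentan is the named permitted background endothelin antagonist (section 5);
- a PDE-5 inhibitor trial of up to 4 weeks is allowed (inclusion 3, exclusion 10);
- bosentan or riociguat within 3 months is excluded (exclusion 11);
- PAH therapy newly started less than 3 months before randomisation is excluded (exclusion 13);
- all prior PAH drugs go on the CRF (section 5.5).

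Assumptions: 3 months is 90 days, and the name test is a literal text match. That TRACLEER is a trade name of bosentan is general knowledge and is not stated in the documents.

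**Formula for a stopped drug.** Take a course of L days whose last dose was g days before the first study dose. Then cmstrt = tr01sdt − (g + L − 1), so V = L + g. Time since stopping counts in the same way as time on drug.

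**Cases compatible with the eligibility criteria, each the subject's only record in the class:**

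| Record | V | Literal result | Listed or named PAH drug in use at entry? |
|---|---|---|---|
| MACITENTAN, ongoing | 120 | On | yes |
| AMBRISENTAN, ongoing | 120 | neither | yes |
| EPOPROSTENOL, ongoing, no start date | none | neither | yes |
| TRACLEER, 30 days, stopped 91 days before | 30 + 91 = 121 | On | no |
| Same history coded BOSENTAN | 121 | neither | no |
| SILDENAFIL trial, 14 days, stopped 169 days before | 14 + 169 = 183 | On | no |
| Unlisted supportive drug only (eg, DIGOXIN) | 200 | neither | no |

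The first row behaves as intended. The second differs from it only in the drug name. Bosentan stopped in line with exclusion 11 has g of at least 90 and L of at least 1, so V is at least 91. It is always On if coded TRACLEER and never placed if coded BOSENTAN. The sildenafil row shows the stop-date problem without relying on the trade name, provided the trial is recorded in this class.

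**What exclusion 13 does to the 28-day cut.** A PAH drug started at least 90 days before randomisation has V of at least 90 + 1 = 91. For a matched term with a start date, an eligible subject is therefore always On, and the cut separates no one. Two apparent faults depend on breaching this criterion:
- Short-course flip: 7 days stopped 10 days before gives V = 17 (naïve), while 7 days stopped 100 days before gives V = 107 (On). The first course began 16 days before first dose.
- Overlap: MACITENTAN with V = 120 plus ILOPROST with V = 10 meets both definitions. The iloprost began 9 days before first dose.

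**Reach into the primary analysis.** Protocol 9.2.1 and SAP 6.3 use the stratum. The sample PHREG code in SAP Appendix 2.1 has treatment alone in the model and no STRATA statement. The overall hazard ratio depends on Appendix 1 only if the model in the protocol or SAP 6.3 is the one run.

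**The case against.** The strongest defence is that, for eligible subjects and matched terms, the rule reduces to ever treated versus never treated, which is coherent. The protocol has no level for previously treated, now untreated subjects, and a subject who once took bosentan is not naïve either. That stands in part: the protocol does not settle the label. It does not rescue the plan, because the SAP states no such convention and calling a stopped drug treatment at entry contradicts the factor's name.

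The production program and the coded terms are also unseen. The list followed a blind data review, a programmer may have corrected the spelling, and SAP 5.5 provides a listing of stratification errors. All true, but the sentence on clinical reality states an aim and gives no rule for an unmatched subject.

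Four stronger readings are tempting and should not be drawn:
- *The categories routinely overlap or flip with time since stopping.* Both need a drug started under 28 days before first dose, which exclusion 13 should make mainly a protocol deviation.
- *Classing a subject randomised as On but with no record as naïve is an error.* All prior PAH drugs should be on the CRF, so this is arguably the correction that SAP 5.5 intends.
- *The rule tests nothing but the start date.* That is true of timing only; it also tests medication class and drug name.
- *Power is lost or an arm is favoured.* The documents give no count of unplaced subjects, and the inputs predate treatment.

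**Conclusion.** The concern holds in a limited form. Followed literally, Appendix 1 fails to place an eligible subject on ambrisentan alone, a subject with only an unlisted term, or one with a listed drug and no start date. It also counts stopped listed drugs as treatment at entry. These are properties of the rule, not frequencies: the number affected is unknown, and the past-bosentan group is narrow because diagnosis must fall within 12 months of randomisation.

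The consequence is confined to the stratified or adjusted estimates, the stratum subgroups and the misallocation listing. No bias between arms is expected, and the interim non-inferiority decision is unaffected. The conclusion rests on a literal name match and, for the stopped-drug cases, on those drugs being recorded in the class that Appendix 1 searches. The rule should be corrected, but the fault does not threaten the trial's main conclusion.

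**What to change.** Before database lock, while the study team is blinded (SAP section 9):

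1. Correct the term to AMBRISENTAN and reconcile the list with every coded term in that class in the blinded data, including generic names such as bosentan and riociguat.
2. Where stop dates are recorded, require a listed drug to be ongoing on Day 1 to count as On, and state one convention for previously treated, now untreated subjects.
3. Let any one qualifying drug make the subject On.
4. Keep the IVRS/IWRS stratum for any subject the rule cannot classify, including those with missing start dates.
5. Run the stratified Cox model with the randomised strata as a sensitivity analysis.

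The cost is a few lines of SAP text, a small change to one derivation and one extra run. Step 2 depends on the CRF capturing stop dates, which the documents do not show; the other steps do not.
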